At the time of enrollment, participants will be asked to consent for release of their medical records for any hospitalization within 1 month following study enrollment.

If a participant is hospitalized within 1 month of study enrollment for any reason, will we request the records of that hospitalization and abstract them for primary and secondary causes of hospitalization. If these causes are deemed respiratory or study drug related, this information will be recorded in the centralized data capture system for the study and subsequently reported to the IRB.

If a participant dies within 1 month of study enrollment, we will request the record for any ED visit or hospitalization leading up to their death and abstract information on causes of death. If these causes are deemed respiratory or study drug related, this information will be recorded in the centralized data capture system for the study and subsequently reported to the IRB.

Table 2. Timing of Trial Data Collection

	Control	Intervention		
Data Items	Enrollment	Enrollment (Day 0)	Follow-up (Day 2/3)	Follow-up (Day 5/6/7)
Informed Consent	X	X		
Participant’s Demographic & SES Characteristic	X	X		
Clinical Data & Health Seeking Behaviors	X	X	X	X
Nasal Swab Collection	X	X	X	X

Molecular Test		X		
Initial gift card	X	X		
IF FLU POSITIVE:				
Antiviral dispensation log	•	X		
Daily symptom questionnaire	•		X	X
Additional \$30 gift card	•	X		
Additional \$5 gift cards	•		X	X

Adverse event reporting

Data on adverse events will be collected from the trial participant for 14 days following drug administration, with day 2/3 and day 5/6/7 symptom logs during the 7-day post-treatment period, followed by a day-14 questionnaire filled out by the participant and follow-up prompting provided by the study committees. See section XI for more details.

Protections against risks

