Data Safety and Monitoring Board: The purpose of the DSMB is to provide external, objective advice to the Executive Committee regarding the safety and efficacy of the interventions being evaluated. This committee will be responsible for reviewing the data from the study on a regular basis, summarizing their conclusions and advice in a written set of minutes, and communicating this information to the Executive Committee. The PI will then forward these minutes to the Institutional Review Boards at the University of Washington. The DSMB has specific responsibility to determine if there are problems relating to the safety of the intervention, to the degree the trial should be stopped, and to determine if the study should be stopped early because the benefit of the interventions has proved to be stronger than originally anticipated. The DSMB will meet just prior to the pre-season enrollment of shelter participants to review the final protocol, and once a year after the beginning of data collection to review accumulated data. Voting membership on the DSMB is limited to persons external to the investigative team. Senior members of the investigative team will serve as ex-officio members without voting rights. The specific composition of the DSMB will include expertise in biostatistics, epidemiology, and clinical infectious diseases. In addition to the voting members of the DSMB, study investigators will act as resources to the DSMB in a non-voting capacity.

As data accumulate, the DSMB will review whether there is enough evidence such that the continuation of the study would not yield any further meaningful data on treatment effects. While we do not believe *a priori* stopping rules are an appropriate approach to decision making in clinical trials (with the exception of evidence of spread for baloxavir antiviral resistance), we recognize that the DSMB may feel differently. If stopping rules are desired by the DSMB we will use those of O'Brien and Fleming. These rules use a conditional power framework and are commonly used in clinical trials.

Plan for reporting unanticipated problems/adverse events:

- **Serious Adverse Events:** Serious adverse events (SAEs) under Good Clinical Practice (GCP) guidelines include death, a life-threatening reaction to the study drug or other study procedure, hospitalization, or significant or persistent disability or impairment.

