- **Other Adverse Events:** This will include any untoward medical event that occurs in a participant, any unfavorable sign or symptom disease temporally associated with the provision of the intervention, or any noxious or unintended response to the study drug. These other adverse events can be anticipated based on what we know about reactions to antiviral medications, or unanticipated. Examples of anticipated adverse events include (but are not limited to) instances of nausea, headache, or diarrhea. Unanticipated adverse events are those

that are either unexpected in terms of nature, severity, and frequency especially if they indicate that there is greater risk of harm than previously recognized.

On days 2/3 and 5/6/7 following receipt of the study drug, all study participants will be asked to complete questionnaires pertaining to evidence of short-term reaction during their interaction with the kiosk study staff, in addition to providing additional nasal swab specimen and daily symptom logs. A final questionnaire to assess for AEs and SAEs will be administered on Day 14. These questionnaires will be monitored daily by the data management team, such that adverse events will be reported in real-time.

All SAEs (regardless of causality), and any grade 3 and 4 AEs which are deemed related or possibly related to the study drug, will be logged in the AE database and reported electronically to the designated principal investigator ([name]) for review within 48 hours . This review will determine if there is any indication for the event being related to the study intervention or procedures. The clinical investigators will review the file and make a determination regarding attribution to study procedures or the intervention.

If the adverse event is considered by the clinical team to be minor in severity, it will be logged in the centralized data capture system and a summary of such events will be reported to the DSMB. If the severity of the adverse event is considered to be moderate or severe by Principal and Co-Principal Investigators, it should be reported to the safety officer (DSMB) and the cognizant IRB immediately. All study-related SAEs will be reported to the IRB within 14 days.

The following are a list of anticipated and unanticipated adverse events we expect to be attributable to the study procedures or the intervention:

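### Section VIII provides for recording hospitalisations and deaths found through records only if the cause is judged respiratory or drug related, while Section XI wants every serious event logged before attribution

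*Combined protocol and SAP*

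**What the plan says.** Section VIII, Intervention follow-up data collection, has two parallel paragraphs. The hospital paragraph opens with "If a participant is hospitalized within 1 month of study enrollment for any reason" and the death paragraph with "If a participant dies within 1 month of study enrollment". Neither limits the record request by cause. Each then carries the same condition on what happens to the abstracted information: "If these causes are deemed respiratory or study drug related, this information will be recorded in the centralized data capture system". Information that meets it is also reported to the IRB. Neither paragraph says who makes the judgement, or what is done with an event that fails it.

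Section XI, in its plan for reporting adverse events, defines serious adverse events (SAEs) to "include death, a life-threatening reaction to the study drug or other study procedure, hospitalization, or significant or persistent disability or impairment". Death and hospitalisation carry no causality condition. It then names what is logged in the AE database and sent to the principal investigator within 48 hours: "All SAEs (regardless of causality), and any grade 3 and 4 AEs which are deemed related or possibly related to the study drug". Relatedness is decided at the review that follows, by the clinical investigators.

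On timing, Section VIII, Adverse event reporting, states: "Data on adverse events will be collected from the trial participant for 14 days following drug administration". Section XI places the last AE and SAE questionnaire on day 14.

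**The concern.** The two sections put the same two steps in opposite orders. Under Section XI an event is logged first and attributed second. Under Section VIII a cause is judged first, and entry depends on the answer. An adverse reaction that nobody expects is the kind of event that a screen on presumed cause can miss, so the order matters.

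At stake is the completeness of the serious-event data. If some hospitalisations and deaths found in records are never entered, all-cause counts after dosing cannot be relied on as complete. A review of safety would then partly rest on a judgement that left no record.

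**Working it through.** No figure in the plan depends on this point, so there is none to reproduce. The check sets the sections side by side and then compares their windows.

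**Step 1. The two rules.**

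| | Section VIII, record abstraction | Section XI, adverse-event plan |
|---|---|---|
| Events in scope | Any hospital stay or death within 1 month of enrolment | Every SAE, so any death or hospital stay |
| Condition on entry | Cause judged respiratory or drug related | None for SAEs; relatedness limits only grade 3 and 4 events |
| Where entered | Central data capture system | AE database |
| Who judges | Not stated | Clinical investigators |
| Order | Judge, then enter | Enter, then judge |
| Event failing the condition | No route stated | Does not arise |

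The documents do not say whether the two databases are the same. Section XI also logs minor adverse events in the central system with no relatedness condition. Read literally, a minor event has a stated place there and a death judged unrelated does not.

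**Step 2. How events reach Section XI.** The inflow described is the questionnaires and symptom logs at day 2/3, day 5/6/7 and day 14. Section VIII says that follow-up visits capture any adverse event, with no filter. An admission reported at one of these contacts is therefore logged under Section XI, whatever its cause.

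**Step 3. The windows.** Inputs: adverse-event collection ends 14 days after the drug (Sections VIII and XI); record abstraction runs 1 month from enrolment (Section VIII). Assumptions: the drug is given on the day of enrolment, and a month is 28 to 31 days.

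- Days without a scheduled adverse-event contact = length of month − 14.
- Short month: 28 − 14 = 14 days; 14 / 28 = 50%.
- Long month: 31 − 14 = 17 days; 17 / 31 = 55%.

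For about half of the month, record abstraction is the only route described.

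**Step 4. Who depends on the record route.**

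- Events after day 14, from step 3.
- Deaths. Section VIII has the participant complete the day-14 questionnaire, which a participant who has died cannot do.
- Treated participants who miss contacts. Section V calls this population transient, and Section III lists loss to follow-up after receiving an antiviral as an outcome, so some missed contacts are expected.

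For these three groups the cause condition in Section VIII comes before the investigators' review, and nothing written sends a screened-out event on to it.

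**The case against.** The strongest reply is that Section VIII does not switch Section XI off. It says what happens if the cause qualifies; it does not forbid logging the rest. It names a different database, and both its own Adverse event reporting paragraph and the follow-up step in Section V point to Section XI for detail. Section XI sets no end date on the duty to log SAEs. The person who judges cause under Section VIII may be the same clinical investigator. Contact within 24 hours of dosing, in-person follow-up and regular kiosk staffing add further chances to hear of an event. The Data Management Plan and the Manual of Operations, which are not among the documents, may settle the routing.

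Much of this stands, and it rules out several stronger readings that a reader might infer:

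- *That serious events are certainly lost, or that the principal investigator and the DSMB never see them.* The documents do not support this, because the Section XI duty remains in force.
- *That an unrelated admission on day 10 is dropped.* If it is reported at a scheduled contact, it has an unfiltered route.
- *That the screen is purely one of causality.* Respiratory events pass it whatever their relation to the drug.
- *That a share of events lost can be stated.* The documents give no rate or cause split for admissions or deaths.
- *That the limit on IRB reporting conflicts with Section XI.* Section XI also limits its 14-day IRB report to study-related SAEs.

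What does not stand is the claim that reading the sections together closes the gap. The instruction specific to abstracted records is the conditional one, and the inflow described for Section XI ends at day 14.

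**Conclusion.** The concern holds in a limited form. Two stated rules conflict on whether cause is judged before or after a hospitalisation or death is recorded, and the plan gives no route to the AE database for events known only through records that fail the Section VIII condition. The exposure is 14 to 17 days of the 1-month window, plus deaths and missed contacts among treated participants. It rests on the month-length and dosing-day assumptions in step 3, and on the documents as they stand without the operational manuals.

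The number of people concerned is probably small, since Section X reports low influenza case counts, but no count of treated participants is given. This is a matter of safety-data completeness. It should be corrected, but it does not touch the primary outcome or the power calculation.

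**What to change.** Reconcile Section VIII with Section XI:

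- In both paragraphs of Section VIII, remove the cause condition on recording. Enter every hospitalisation and death found within 1 month of enrolment, with cause and attribution as recorded fields.
- Send those in treated participants through the investigator review in Section XI, and name the AE database as the destination.
- Leave the relatedness limit on IRB reporting in place, since it agrees with the 14-day rule in Section XI.

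This version is dated March 2022 and enrolment was projected to end in April 2021, so new wording alone changes nothing in the data. Apply it by checking the retained abstracted records against the AE database and entering what is missing. Section VIII keeps primary data sources for at least 5 years after the primary publication, so the check should be feasible.

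The cost is a modest amount of retrospective entry and investigator review. The record request already covered every cause, so no wider request is needed. The resulting counts will still cover only events that the study learned of and participants who agreed to release their records, and the report should say so.

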The trial is being conducted in nine homeless shelters in the Seattle, WA metropolitan area. The aim is to enroll nine shelters, each with a nightly population of between approximately 45 to 212 individuals for a total number of a maximum 1,696 individuals under surveillance each influenza season. We will conduct this trial over two influenza seasons with re-randomization of the shelters each season for timing of the intervention. The University of Washington is the sponsor of the trial which is supported by an anonymous funder who does not have any ownership over the management and conduct of the study, the data, or the rights to publish.

III. Objectives

The objective of the trial is to evaluate the efficacy of on-site testing and rapid antiviral treatment with baloxavir or oseltamivir in influenza-positive individuals for prevention of secondary cases of influenza virus infection within homeless shelters.

Primary Outcome Measure

The primary outcome measure will be the incidence of cases of influenza in shelters during the intervention period compared to the incidence of cases during the control period. It will be calculated as the number of cases of laboratory-confirmed influenza among shelter residents divided by the number of unique shelter residents tested. The incidence during intervention periods will be compared to the incidence during non-intervention periods using a generalized linear mixed model to control for clustering, differences in shelters, and time period.

Secondary Outcome Measures

Feasibility and adherence outcomes

- Feasibility of implementation of point-of-care molecular testing and treatment of influenza in shelters (time between symptom onset until diagnosis)
- Feasibility of implementation of influenza treatment in shelters (time between symptom onset until treatment)
- Proportion of participants that become lost to follow-up (after testing positive for influenza at baseline enrollment and receiving an antiviral)
- Proportion of participants that show non-compliance with study drug (only applicable to oseltamivir)

Clinical outcomes

- Symptom type, duration and severity among viral positive cases (including broken down by influenza sub-type)
- Prevalence of asymptomatic and pauci-symptomatic influenza-positive cases
- Proportion of laboratory-confirmed influenza cases that report fever
- Relationship between symptom type, duration and severity, and current seasonal influenza vaccination status

Laboratory outcomes

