Person-to-person transmission: We will use the CDC definition for influenza transmission that refers to the ability of an influenza virus to spread from one person to another, most commonly through large or small droplets containing influenza virus that are expelled when a sick person is coughing or sneezing.

Homelessness: We will use a truncated version of the definition provided by the U.S. Department of Housing and Urban Development that identifies people who are living in a place not meant for human habitation, in emergency shelter, in transitional housing, or are exiting an institution where they temporarily resided if they were in shelter or a place not meant for human habitation before entering the institution.

X. Statistical analyses

Due to the SARS-CoV-2 pandemic onset and corresponding methodological changes, the primary outcome measure for this study will only be calculated based on data collected from Year 1. Standard surveillance beginning on March 30, 2020 expanded to include the testing of study staff and

asymptomatic individuals 3 days per week. The primary outcome measure will be calculated excluding asymptomatic individuals and shelter staff tested as part of the modified standard surveillance methodology initiated on March 30, 2020. As shelter managers were unable to provide us with reliable daily census, we were unable to establish person-days at risk for this study population. Instead, we will use unique participants as the primary unit of analysis. Overall, data collected between November 15, 2019 and March 31, 2021 will be used for data analysis.

Primary Outcome Measure

1. **Cumulative incidence** of cases of influenza (A and B) in shelters during the intervention period compared to the control period.
 - a. As daily census counts for participating shelters were not made available to the research team, person-days and therefore incidence rates will not be calculable. Cumulative incidence instead will be calculated as the number of cases of laboratory-confirmed influenza among shelter residents divided by the number of unique shelter residents tested.

Endpoint: Number of influenza-positive events in the control v. intervention periods

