Statistical analysis: Shelters will be analyzed with an intent to treat analysis to preserve the advantages of randomization. The number of influenza-positive tests will be analyzed using a generalized linear mixed model following a Poisson distribution with a log link and robust variance. The model is adjusted for calendar time and an exposure time variable based on shelter capacity. It will be used to calculate the relative risk of infection during the intervention period compared to prior to intervention, 95% confidence intervals, and p-value.

This model includes symptomatic individuals who tested throughout Year 1 of the study (November 15, 2019 – March 31, 2020).

Despite operational futility, descriptive statistics (counts, proportions, and appropriate measures of dispersion) for **both years 1 and 2** will be provided for the following Secondary Outcome Measures; additional statistical models will not be run due to low influenza case counts and the impact of the SARS-CoV-2 pandemic:

1. Feasibility of implementation of point-of-care molecular testing and treatment of influenza in shelters
 - a. Proportion of participant encounters with time between symptom onset until diagnosis with RT-PCR <48 hours in each study period
2. Feasibility of implementation of influenza treatment in shelters
 - a. Proportion of influenza-positive participants identified through on-site molecular testing in the intervention period that were treated with an antiviral
3. Proportion of participants that drop out of study
 - a. Measured as dropping out after providing consent
4. Proportion of participants that show non-compliance with study drug

- a. Only applicable to those that receive oseltamivir rather than baloxavir which is a single-dose antiviral. Measured based on self-report during follow-up visits with study research assistants.
5. Proportion of laboratory-confirmed influenza cases that report fever, or feverishness
 - a. Based on self-report, not gold standard measurement
6. Influenza viral RNA levels
 - a. Measured mean cycle threshold value for each laboratory-confirmed influenza-positive specimen collected at baseline enrollment
7. Proportion of samples with detectable influenza RNA virus at days 2/3 and days 5/6/7
 - a. Provided subject has not become lost to follow up

XI. Data Safety and Monitoring

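### The primary model (positive tests per shelter capacity) does not estimate the declared primary outcome (cases per resident tested), and its event is not tied to a case

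*Combined protocol and SAP*

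**What the plan says.** Section III (Primary Outcome Measure) defines the outcome as "the number of cases of laboratory-confirmed influenza among shelter residents divided by the number of unique shelter residents tested". It adds that a generalized linear mixed model will compare this quantity between intervention and non-intervention periods.

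Section X repeats the ratio, calls it cumulative incidence, and explains that person-days could not be obtained because reliable daily census counts were lacking. Its stated replacement is: "Instead, we will use unique participants as the primary unit of analysis". Directly below, it gives a count: "Endpoint: Number of influenza-positive events in the control v. intervention periods".

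The statistical analysis paragraph of section X then says: "The number of influenza-positive tests will be analyzed using a generalized linear mixed model", with a Poisson distribution and log link. On exposure: "The model is adjusted for calendar time and an exposure time variable based on shelter capacity". On the output: "It will be used to calculate the relative risk of infection during the intervention period compared to prior to intervention", with its confidence interval and p-value. On the population: "This model includes symptomatic individuals who tested throughout Year 1 of the study".

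Section II (Study Design) still states the primary outcome per person-day, which section X says cannot be calculated.

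**The concern.** A reader of section III expects the relative risk to compare cases per resident tested. The model in section X has no term for the number tested, and no section says how its result relates to the declared ratio. The p-value for the primary hypothesis is thus attached to one quantity while another is named as the outcome.

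The labels add to the difficulty. Cases divided by symptomatic residents tested is the proportion positive among those tested. It is not cumulative incidence in the shelter, because residents who were not tested are not in the denominator. Readers will set a relative risk of infection beside two such proportions and take it as a comparison of them.

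The event is also loose: section X speaks of cases, of positive events and of positive tests. Under section V (Follow-up) and Table 2, repeat swabs at days 2/3 and 5/6/7 are scheduled only for positives in the intervention period. If they entered the count, they would add events on one side only and bias the relative risk against the intervention.

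**Working it through.** **The plan's own figure.** The documents give no number for the gap between the two quantities. The nearest figure is in Sample size: 86% power for a risk ratio of 0.50 with 18 shelter-seasons and 200 people per shelter. A stepped-wedge weighted least squares calculation with the stated inputs (1.6% per month, SDs .0028 and .0032, six months, two-sided 0.05) gives 84.7% to 84.9%, within 2 points of 86%. It assumes four monthly crossover steps after one all-control month, since Figure 2 is not shown. That calculation rests on shelter census, not on residents tested. Below, 0.50 serves only as an example.

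**The definitions side by side.**

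| Place | Numerator | Denominator |
|---|---|---|
| Section II | cases | person-days |
| Sections III and X, outcome | cases | unique residents tested |
| Section X, endpoint line | positive events | none stated |
| Section X, model | positive tests | exposure based on shelter capacity |

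The model wording leaves open whether capacity is an offset or a covariate. In neither case does the number tested enter.

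**Size of the gap.** Take capacity-time as an offset. Let k be the ratio, intervention to control, of residents tested per unit of capacity-time, equal across shelters and months. Then

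RR(tested) = RR(capacity) / k.

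The documents give no k, so 0.6 to 1.5 is assumed. For RR(capacity) = 0.50:

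- k = 0.6: 0.50/0.6 = 0.83
- k = 0.8: 0.50/0.8 = 0.63
- k = 1.25: 0.50/1.25 = 0.40
- k = 1.5: 0.50/1.5 = 0.33

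Poisson fits to expected counts check this. They used nine shelters, five calendar periods of 16, 31, 31, 29 and 31 days (138 days, November 15 to March 31), and month and shelter effects, with shelter effects fixed rather than random. The capacity offset returned 0.500 for every k. The tested offset returned 0.833, 0.625, 0.500, 0.400 and 0.333 for k = 0.6, 0.8, 1, 1.25 and 1.5.

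**Which denominator misleads.** Suppose there is no true effect, and that testers gained or lost under the intervention are q times as likely to be positive as control-period testers on average. Then RR(capacity) = 1 + (k − 1)q, and RR(tested) is that value divided by k.

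| q | RR(capacity), k = 0.6 / 1.5 | RR(tested), k = 0.6 / 1.5 |
|---|---|---|
| 1 | 0.60 / 1.50 | 1.00 / 1.00 |
| 0.5 | 0.80 / 1.25 | 1.33 / 0.83 |
| 0 | 1.00 / 1.00 | 1.67 / 0.67 |

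For example, at k = 0.6 and q = 0.5: 1 − 0.4 × 0.5 = 0.80, and 0.80/0.6 = 1.33. The bias passes from one denominator to the other as q changes, and the documents do not give q.

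**Direction of k.** It is open. An on-site result and the $30 card could raise testing. Required consent to drug and follow-up could lower it, although the Summary keeps decliners in surveillance. Less illness would lower it too.

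**The event.** Three features suggest that repeat swabs are not meant to count: the unique-participant unit, the separate follow-up survey in section VIII, and the separate secondary outcome for those swabs. Against that, section X restricts specimens to baseline enrollment for the RNA-level outcome but not for the primary model. The 14-day episode rule in section IX is written for influenza-like illness, not for influenza cases.

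**The case against.** The strongest reply is that capacity stands in for the missing census, so the model is a sensible fallback and fits the count given on the endpoint line. That is fair as a defence of the model. It does not make the model estimate the outcome that sections III and X declare, and section X names unique participants, not capacity, as its replacement for person-days.

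A second reply is that 0.83 to 0.33 is an identity applied to an assumed k. This stands: the range shows sensitivity and is not an estimate of the trial's error.

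A third is practical. The model uses Year 1 only, about nine shelter-seasons. At a risk ratio of 0.50 the power table gives 52% for 8 and 72% for 12, and section X itself cites low case counts. The interval will be wide on either denominator. This limits the consequence but does not remove the mismatch.

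Three stronger readings are tempting, and the documents do not support them.

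- A reader might infer that follow-up swabs will be counted. Nothing says so; the text only fails to exclude them.
- A reader might infer that the capacity model is the biased one and the tested ratio the sound one, or the reverse. That depends on q, which is unknown.
- A reader might count the gap between a calendar-adjusted relative risk and a crude ratio as part of the fault. That gap is expected in a stepped wedge, and section III announces adjustment for time period.

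**Conclusion.** The plan is wrong as written on this point and should be fixed. If it is followed, the primary relative risk, confidence interval and p-value describe positive tests relative to shelter capacity, while the declared outcome is cases per resident tested. This conclusion rests on the text alone and is held with high confidence.

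The size is conditional. With a capacity-time offset and a uniform k between 0.6 and 1.5 (an assumption), a capacity-based 0.50 corresponds to anything from 0.83 to 0.33 on the tested denominator. With no true effect, either measure can stray from 1.00 depending on q, so neither can be called unbiased. For follow-up swabs only a direction is claimed, and only if they were counted.

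**What to change.** 1. Reconcile sections II, III and X. State that the model estimates the ratio of influenza-positive residents per unit of shelter-capacity-time and that capacity-time enters as a log offset. Do not present the result as the ratio of cases to residents tested. Remove the person-day definition.
2. Relabel cases over unique residents tested as the proportion positive among symptomatic residents tested. Beside the capacity model, report the same calendar-time-adjusted mixed model with log(unique residents tested in the shelter-period) as offset; cells with nobody tested drop out. Give both results and claim freedom from ascertainment bias for neither.
3. Use one event in both models: each resident at most once per shelter-period, from an enrolment swab, by the same laboratory RT-PCR in both periods, with day 2/3 and 5/6/7 swabs excluded. State how a resident tested in both periods is counted.
4. Tabulate unique residents tested and capacity-time by shelter-period, noting that a change in testing may reflect less illness as well as changed uptake.
5. Disclose that the clarification was made after data collection. This version is dated March 19, 2022, and the analysis data end on March 31, 2021.

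The cost is wording, one additional model and one table from data in hand. The drawbacks are that the two models may disagree, both will be imprecise with few cases, capacity is only a proxy for occupancy, and the change is post hoc.
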